#### **5.4 TOXICITY CRITERIA**

This study will utilize the Common Terminology Criteria for Adverse Events (CTCAE) version 3.0. CTCAE version 3.0 can be downloaded from the CTEP homepage at <http://ctep.info.nih.gov/>. All appropriate treatment areas should have access to a copy of CTCAE version 3.0.

### **6 STATISTICAL CONSIDERATIONS**

#### **6.1.1 Racial/gender make-up**

Subjects from both genders and all racial/ethnic groups are eligible for this study if they meet the eligibility criteria outlined in section 2.1. To date, there is no information that suggests that differences in drug metabolism or disease response would be expected in one group compared to another. Efforts will be made to extend accrual to a representative population, but in this preliminary study, a balance must be struck between patient safety considerations and limitations on the number of individuals exposed to potentially toxic and/ or ineffective treatments on the one hand, and the need to explore gender and ethnic aspects of clinical research on the other hand. If differences in outcome that correlate to gender or to ethnic identity are noted, accrual may be expanded or a follow-up study may be written to investigate those differences more fully. As a practical matter, it should be noted as outlined in the background section, that the demographics of the AIDS epidemic are shifting in the United States. Currently, the largest growing population is African-American women. It is difficult to predict how these changing demographics will affect accrual for this particular protocol, but patients from minority populations are disproportionately affected by HIV disease and thus efforts to inform minority communities about this study will be a priority in the recruitment effort.

#### **6.1.2 Age Exclusion**

Children under 18 years of age are excluded from the study. AR-PCNSL in children is extremely rare, and comprises less than 1% of all cases of AR-PCNSL. For example,

only 1 child was reported with AR-PCNSL in 1996. The incidence of vertical transmission of HIV in the United States has become extraordinarily low and in 2003, 147 cases of perinatal HIV infection were documented and only 161 cases of HIV/AIDS were diagnosed in those 13 years of age or under. The estimated number of AIDS cases in this age group was only 59 for 2003. The study requires multiple invasive procedures and is not designed to assess the tolerability of the treatments in young children. However, if the preliminary study results are favorable, and pediatric cases with AR-PCNSL otherwise eligible for the study except for age criteria come to our attention, if appropriate, the study may be amended after discussion with the NCI IRB if the risks and benefits appear to be in favor of including children on the study.

#### 6.1.3 Sample Size and Accrual Limits

The primary objective of this study is to preliminarily estimate the magnitude of, and determine if there is potentially an acceptable fraction of, patients with primary brain lymphoma, who will receive the experimental treatment consisting of HAART with high-dose methotrexate-rituximab who are able to survive without recurrent lymphoma or severe cognitive problems (as defined by Neurological Function Class 3 in [Appendix 2](#)) for at least two years.

The goal of this limited size pilot trial is to enroll 15 evaluable patients who receive all treatment, including high-dose methotrexate. With conventional treatments, including whole brain irradiation, it would be expected that only 25-30% of all such patients with this disease would be alive without recurrent brain lymphoma and free of cognitive problems at the end of two years (a satisfactory result, but in too small a fraction of patients). We believe it quite possible that by using this particular chemotherapy, as many as 65% would be alive without recurrent lymphoma and without cognitive problems after two years. Sixty five percent is a figure chosen that is within range of the outcome expected in high-risk patients with non-AIDS primary brain lymphoma treated with high-dose methotrexate based strategies. With 15 patients, using a one-sided 0.1 alpha level exact test of binomial proportions, there is 88% power to rule out 30% with a satisfactory result after two years in favor of 65% with a satisfactory result. Should the results appear at all promising, even if not to this degree, the strategy may be taken to the AIDS Malignancy Consortium to see if they are interested in pursuing the idea in a larger, more definitive fashion. The results of this study will be weighed against the best available data from other studies to make a reasonable determination as to how to proceed with or modify this approach for further development.

Additionally, up to 10 additional patients who are not eligible to receive high-dose methotrexate may be accrued in the “Radiation-sparing Best Available Care” Cohort. The patients enrolled in this limited size cohort will be evaluated for the same endpoints as in the main cohort receiving high-dose methotrexate, but given the limited number of patients who will enroll into this cohort, all analyses in this cohort will be considered hypothesis generating and exploratory. Accrual to this cohort will close when 15 evaluable patients have been enrolled in the main cohort.

All secondary endpoints will be evaluated using explorative techniques, and will be reported as exploratory, since the study is not designed to address any of these points with more than minimal power.

Since part of the treatment strategy is aimed at HIV suppression and immune reconstitution, up to 3 patients who are non-adherent with HAART within the first 9 months of therapy may be replaced. It can often take up to 9 months to adjust medications for purposes of optimizing medication tolerance and adherence to antiretroviral therapy. Patients who are clearly non-adherent and thus are unable to maintain an HIV viral load of <5000 copies HIV mRNA/mL plasma and do not have an increment in the CD4+ cells to above 75/mm^3 by the end of 9 months may be replaced. Patients who maintain lower HIV viral loads but do not have adequate immune recovery will not be replaced, and will be considered treatment failures in the event of tumor recurrence. Informal comparison will be made between those who are HAART naive at entry and those who are antiretroviral experienced.

This is a rare condition, and it is expected to take between 6 and 10 years to enroll 15 patients onto this trial in the main cohort and up to 10 in the cohort not receiving high-dose methotrexate. Up to three patients may be replaced if during the first 9 months they are clearly non-adherent with HAART as described above. Thus an accrual ceiling of 28 patients will be used.

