## 1 INTRODUCTION

### 1.1 STUDY OBJECTIVES

#### 1.1.1 Primary

1.1.1.1 The primary objective of this study is to preliminarily estimate the fraction of patients with primary brain lymphoma receiving experimental treatment consisting of HAART with R-HD-MTX who are alive and without recurrent lymphoma or severe cognitive problems (as defined by Neurological Function Class 3 in Appendix 2) at two years. It will also be important to determine if this fraction may be sufficiently high for further investigation.

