Encouraging data on the utility of unlabeled rituximab in AIDS-unrelated PCNSL has been reported in small studies. Since CNS lymphoma has a predisposition for perivascular infiltration that disrupts the blood brain barrier, greater anticancer agent penetration into areas of the brain affected by tumor are seen when compared to surrounding normal brain, as shown in biopsy and autopsy specimen in studies addressing this. Indeed, there is mounting clinical experience that rituximab can be useful in primary brain lymphoma when administered intravenously. In small studies of refractory PCNSL, responses have been seen in the majority of treated patients who received rituximab monotherapy or rituximab in combination with cytotoxic agents. Although reports that rituximab monotherapy in previously treated refractory-relapsed PCNSL results in clinical and radiographic responses suggests that rituximab can penetrate into areas of bulky disease in the brain, there is insufficient data to know with certainty what the overall contribution of rituximab is in the combination chemotherapy setting. However, PCNSL experts have supported its clinical trials development. The Cancer and Acute Leukemia Group B trial 50202 entitled “Intensive Chemotherapy and Immunotherapy in Patients with Newly Diagnosed Primary CNS Lymphoma” is a multi-institutional study further investigating rituximab combining it with high-dose methotrexate and temozolomide. Thus, there is well-established precedent for investigating the use of rituximab in PCNSL in the HIV unrelated setting. Likewise, rituximab may be a promising agent in AIDS-related PCNSL as

articulated above. The core regimen in this protocol will thus investigate the use of leucovorin protected high-dose methotrexate with rituximab and HAART.

Rituximab will be omitted from cycles 7 and 8. The rationale for this is that only patients who have achieved a complete response will receive the additional two cycles. Therefore, it is assumed that rituximab penetration into the area previously affected by obvious tumor will become insufficient due to improved blood-brain barrier integrity. However, it may be beneficial to administer additional high-dose methotrexate cycles with increased dose-intervals in order to help prevent early tumor recurrence while allowing for additional time for greater immunologic recovery.

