### Arms

Number	Name	Description
1	Single arm	Induction treatment cycles with rituximab, high-dose methotrexate and leucovorin will be administered every 2 weeks for 6 cycles. Two additional consolidation cycles of high-dose methotrexate without rituximab will be administered at 4 weeks and 8 weeks following completion of the combined therapy.

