**Figure 1: Study Schema: Eligibility Evaluation and Initial Therapy**

### **3.2 PHASE II STUDY DESIGN FOR HIGH-DOSE METHOTREXATE WITH LEUCOVORIN RESCUE AND RITUXIMAB**

Induction treatment cycles with rituximab, high-dose methotrexate and leucovorin will be administered every 2 weeks for 6 cycles. Two additional consolidation cycles of high-dose methotrexate without rituximab will be administered at 4 weeks and 8 weeks following completion of the combined therapy.

MRI will be repeated at the end of cycles 2, 4, 6, and 8, and additionally as clinically indicated. At the time of first evidence for complete tumor response by MRI criteria, FDG-PET scan and EBV DNA assessments of the blood and CSF will be repeated. If there is not a complete response by end of cycle 6, patients will be categorized as treatment failures and will not receive the two additional high-dose methotrexate doses. At end of treatment, restaging by MRI will be performed once every 2 months x 3; then once every 3 months x 6; then once every 6 months x 2; then as clinically indicated or annually up to year 5. After this period, clinical evaluations may continue and restaging

performed if clinical suspicion of CNS pathology. Additionally, FDG-PET scan will be repeated as outlined in section 3.8.4.2. (See also Appendix 3).

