3.4.2 High-dose methotrexate

3.4.2.1 The creatinine clearance (CrCl) will be calculated by method of Cockcroft-Gault prior to each cycle (see [Appendix 4](#)). If CrCl is  $\geq 100$  mL/min, then no dose adjustment is necessary. If CrCl is  $< 100$  mL/min, then the methotrexate dose is adjusted by the fraction of CrCl less than 100 mL/min (e.g., methotrexate dose =  $6000 \text{ mg/m}^2 \times \text{CrCl}/100$ ).

3.4.2.1.1 For estimated creatinine clearance  $< 100$  mL/min, a 24-hour urine collection should be obtained *plus* a serum creatinine at the end of the collection period to determine a measured creatinine clearance.

3.4.2.2 Delayed methotrexate serum clearance ( $> 3$  days after methotrexate infusion) may occur and mandates accelerated rescue and continued hydration and alkalinization. The minimum interval between achieving a serum methotrexate level  $\leq 0.05 \text{ mcg/mL}$  and the start of a subsequent treatment cycle is 7 days.

3.4.2.3 For creatinine clearance  $< 60$  mL/min, no methotrexate will be administered. Administer rituximab without methotrexate after discussion with a medically responsible investigator if renal function cannot be expected to be optimized (CrCl  $\geq 60$  mL/min) within 3 days.

3.4.2.4 For transient ALT and/or AST elevations  $\geq 10X$  the upper limit of normal, withhold methotrexate until both ALT and AST are  $\leq 5X$  the upper limit of normal, then permanently reduce methotrexate dosage by 25% for all subsequent cycles beginning with the next cycle.

3.4.2.5 For ANC  $< 1000 \text{ cells/mm}^3$ , delay methotrexate until ANC recovers to  $\geq 1000/\text{mm}^3$ .

3.4.2.6 For platelet counts  $< 50,000/\text{mm}^3$ , delay methotrexate until platelet count recovers to  $\geq 50,000/\text{mm}^3$ .

3.4.2.7 For any other Grade 3 or greater toxicities related to methotrexate, with the exception of hematologic toxicity, hold methotrexate until toxicity abates to Grade  $\leq 2$ .

3.4.2.8 For pulmonary toxicity related to methotrexate, permanently discontinue methotrexate.

3.4.2.9 Note, if toxicity attributed to methotrexate prevents subsequent methotrexate treatment prior to the time of complete response, patient will be considered a treatment failure. Failure of toxicity to resolve and thus creating dose delays in excess of 15 days will result in methotrexate discontinuation.

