### **3.5 CRITERIA FOR DISCONTINUING RITUXIMAB AND HIGH-DOSE METHOTREXATE WITH LEUCOVORIN RESCUE**

- 3.5.1 Completion of therapy
- 3.5.2 Delayed methotrexate clearance due to impaired renal function, requiring glucarpidase
- 3.5.3 Creatinine clearance <60 mL/min based on a 24-hour urine collection that cannot be corrected within 2 weeks
- 3.5.4 Any creatinine clearance <30 mL/min based on 24-hour urine collection.
- 3.5.5 Inability to tolerate required intravenous hydration (minimum 60 hours of intravenous fluid at a rate  $\geq$ 100 mL/hour)
- 3.5.6 Dose delays in excess of 15 days
- 3.5.7 Withdrawal of consent.
- 3.5.8 Inability to administer to HAART or other oncologic therapies.
- 3.5.9 Progressive neurologic symptoms attributed to progressive AR-PCNSL
- 3.5.10 Untreatable concurrent illness
- 3.5.11 Methotrexate with leucovorin rescue may be discontinued, if in the opinion of the PI or LAI, the risk of continued therapy outweighs the potential benefit of continued therapy, or if patient non-adherence interferes with study objectives.
- 3.5.12 Patients who discontinue Rituximab and methotrexate with leucovorin rescue may continue with “Radiation-sparing Best Available Therapy”, including dose-dense Rituximab, if clinically indicated.

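### Section 6.1.3 does not define 'evaluable', and three sections differ on who is replaced and never say whether replaced patients count in the primary result

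*Combined protocol and SAP*

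**What the plan says.** Section 1.1.1 takes as its target "the fraction of patients with primary brain lymphoma receiving experimental treatment consisting of HAART with R-HD-MTX" who are alive at two years with neither recurrent lymphoma nor severe cognitive impairment. Section 6.1.3 describes the sample: "The goal of this limited size pilot trial is to enroll 15 evaluable patients who receive all treatment, including high-dose methotrexate". It tests 30% against 65% with a one-sided exact binomial test at 0.10 and states 88% power. The rule that closes the second cohort again refers to 15 evaluable patients. 'Evaluable' is not defined for the primary endpoint; in sections 3.6.3 and 3.7 it concerns who can stay on study for neurocognitive or survival follow-up.

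Several sections class patients who do not finish as failures. Section 3.2, on those without a complete response by the end of cycle 6: "patients will be categorized as treatment failures and will not receive the two additional high-dose methotrexate doses". Section 3.4.2.9: "if toxicity attributed to methotrexate prevents subsequent methotrexate treatment prior to the time of complete response, patient will be considered a treatment failure". Sections 3.7 and 3.10.1 count radiotherapy as failure, and 5.3.6 adds death, progression and stopping chemotherapy. Patients can also leave the full regimen and remain under observation. Section 3.4.2.3 provides, in one renal setting, "Administer rituximab without methotrexate after discussion with a medically responsible investigator", and 3.5.12 says "Patients who discontinue Rituximab and methotrexate with leucovorin rescue may continue with" the radiation-sparing alternative.

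Replacement appears in three places:
- **6.1.3:** as many as three patients non-adherent to HAART in the first 9 months, identified by viral load and CD4 count. Relapse is not required.
- **7.1.1:** as many as three non-adherent patients with high viral load, no immune recovery and a lymphoma relapse within 9 months.
- **1.2.5:** patients whose viral load is not kept low and who then have HIV complications that can affect cognition are 'censored' and can be replaced. The detail is left to the statistical section.

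The statistical section does not say whether a replaced patient remains in the analysis.

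**The concern.** A single-arm proportion needs a denominator that is fixed before outcomes are known. Here the only permitted removal happens after treatment starts and depends on events tied to the endpoint: relapse in 7.1.1, and complications bearing on cognition in 1.2.5. 'Censored' has no defined meaning for a binomial proportion at two years. Under 3.11.2, refusal to adhere to HAART also takes a patient off study, so two-year status may be unknown for the patients in question.

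With about 15 patients, three removals can move the result across the plan's own 0.10 level. Two analysts following the text could report different primary results from the same data. Accrual is expected to take 6 to 10 years, so the choice could be made after outcomes have been seen.

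**Working it through.** **Inputs, all from 6.1.3:** n = 15; null rate 0.30; alternative 0.65; one-sided exact test at 0.10; stated power 88%; up to 3 replacements; up to 10 in the second cohort; ceiling 28. X is the number of successes, X ~ Bin(n, p).

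**1. The stated design.** The cut-off is the smallest r with P(X ≥ r | n = 15, p = 0.30) ≤ 0.10.
- r = 7 gives 0.131, which is too high.
- r = 8 gives 0.050.
- Power: P(X ≥ 8 | 15, 0.65) = 0.887.

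The 88% reproduces. The protocol does not state the cut-off of 8; it is derived here.

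**2. The ceiling.** 28 = 15 + 10 + 3. The three spare places match the HAART replacements, and none is left for replacing patients who stop treatment early.

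**3. Error rate if replaced failures are dropped.** Suppose k patients are replaced, all k are failures, and at least 8 of the remaining 15 is still the rule. The dropped patients contribute no successes, so passing is the same event as at least 8 successes among all 15 + k treated. The worst-case chance of passing at a true 30% is P(X ≥ 8 | 15 + k, 0.30):

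| k | treated | chance of passing |
|---|---|---|
| 0 | 15 | 0.050 |
| 1 | 16 | 0.074 |
| 2 | 17 | 0.105 |
| 3 | 18 | 0.141 |

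Two or three replacements can exceed 0.10. These are upper bounds, because they assume that k failures are always available and are the patients replaced.

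**4. One data set, two results.** Take 8 successes with three patients replaced. Excluding the three gives 8/15 = 53%, p = 0.050. Counting them as failures gives 8/18 = 44%, p = 0.141.

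**5. Cut-offs if replaced patients are counted.** For each n, take the smallest r with P(X ≥ r | n, 0.30) ≤ 0.10. Power is shown for two extremes: replaced patients succeed at 65% like the rest, P(X ≥ r | n, 0.65); or they are certain failures and the other 15 succeed at 65%, P(X ≥ r | 15, 0.65).

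| n | cut-off | exact alpha | power, all at 65% | power, replaced all fail |
|---|---|---|---|---|
| 15 | 8 | 0.050 | 88.7% | 88.7% |
| 16 | 8 | 0.074 | 93.3% | 88.7% |
| 17 | 9 | 0.040 | 90.1% | 75.5% |
| 18 | 9 | 0.060 | 94.0% | 75.5% |

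**The case against.** A reader might infer something stronger: that 'receive all treatment' confines the 15 to patients who finish every cycle, and so selects on response. The arm description in 2.4 includes the last two cycles ("Two additional consolidation cycles of high-dose methotrexate without rituximab will be administered at 4 weeks and 8 weeks"), and 1.2.4.3 says "only patients who have achieved a complete response will receive the additional two cycles". The documents do not support that reading:
- Sections 3.2, 3.4.2.9, 3.7, 3.10.1 and 5.3.6 class these patients as failures, and 3.7 says this applies to the statistics. They can be failures only if they are in the denominator.
- A patient without a complete response after six cycles has received all the treatment the protocol assigns.
- Section 6.1.3 ties the 15 to enrolment and goes straight on to patients who cannot receive methotrexate, so the natural contrast is between regimens.
- The ceiling leaves no places for replacing non-completers.

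No error rate is therefore attached to that reading. What stands is that 6.1.3 leaves the reader to work this out.

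On replacement, the best defence is that the intent can be inferred. Section 6.1.3 says that patients with lower viral loads but poor immune recovery are not replaced and count as failures if the tumour recurs. With 'censored' in 1.2.5, this suggests that replaced patients leave the count. HAART is also part of the regimen, so a result among adherent patients has some interest. Both points are fair, and they justify reporting that result too. But the rule is inferred by contrast and not stated, and under 7.1.1 it would remove patients who have already failed the endpoint.

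Finally, this is a pilot. Section 6.1.3 calls its aim preliminary, would consider taking the strategy further on weaker results, and will weigh other data. So the cut-off alone does not decide further development. The fraction and its exact test are still the primary result.

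**Conclusion.** The point holds as a gap in definition and a conflict between sections, and should be fixed. The sample-size calculation is correct. For patients who stop treatment early, the documents imply inclusion as failures, and 6.1.3 only needs to say so. For replaced patients, the three sections give different conditions and none says whether they count.

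The size depends on how many are replaced. With none, the stated design is unaffected. With one, the worst-case error of 0.074 stays within 0.10. With two or three it reaches 0.105 or 0.141. These figures assume that every dropped patient is a failure and that 8 of 15 is kept. The first assumption is true by definition under the relapse condition in 7.1.1, but is only a worst case under the wording of 6.1.3.

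**What to change.** Replace the sample sentence in 6.1.3 with:

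> The primary denominator is every patient assigned to the main cohort who receives any dose of rituximab or high-dose methotrexate under the protocol regimen; patients who do not complete treatment or who move to other therapy stay in the denominator.

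Then:
- Report the result both with replaced patients counted (as failures where they relapsed or their two-year status is unknown) and with them excluded. At minimum, the counted version must be pre-specified, and no patient who has already met a failure criterion such as relapse may be removed from the primary analysis.
- State the cut-offs: 8 at n = 15 or 16, and 9 at n = 17 or 18.
- Reconcile the replacement conditions in 1.2.5, 6.1.3 and 7.1.1, and replace 'censored' with a stated handling.

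This settles the denominator only. Whether a patient who stopped chemotherapy under 5.3.6 but is alive and well at two years is a failure for the endpoint in 1.1.1 needs a separate answer.

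The cost is wording and one extra analysis. The planned 15 patients and the ceiling of 28 do not change. The reported fraction may be lower. If replaced patients count as certain failures, power stays at 88.7% with one replaced and falls to 75.5% with two or three.

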It should be noted that rituximab is not considered at present to be a standard of care in HIV-associated lymphomas, and it appears to be associated with excess morbidity and mortality when used with CHOP chemotherapy for peripheral ARL, especially for patients with advanced CD4+ depletion. The NCI sponsored AIDS Malignancy consortium has reported published results of a large multicenter trial of ARL in which all patients received HAART and CHOP and were randomized to receive rituximab or not. Treatment related deaths occurred in 14% on the rituximab arm compared to 2% of those not receiving rituximab. Moreover, the complete response rate was not different between the two arms, and survival was not improved. Thus, there was excess treatment-related mortality without sufficient evidence of benefit in this trial. Subset analysis suggested that there may have been a subset of patients for whom a benefit could be realized, but the study was not designed to assess this with scientific validity. In contrast, positive benefit of rituximab in ARL has been reported in pooled results of three phase 2 trials of R-iCDE (rituximab with infusional cyclophosphamide, doxorubicin, and etoposide). The complete response rate of 70% was quite high (substantially higher than that previously seen with CDE alone), but again there was evidence of excess treatment-related deaths with approximately 20% of patients having non-fatal infectious complications. For these reasons, some experts have now recommended that rituximab not be used in ARL as standard practice, but that additional investigational studies are needed to better understand the role of rituximab in AIDS (Yarchoan et al, Nat. Onc. in press). Experience from the transplant setting is also in evaluating rituximab in immunocompromised patients. High-dose rituximab of up to 1000 mg/m^2 has been reported to be potentially more effective than standard dose in high-risk lymphoma patients being treated with bone marrow transplant, a finding that also emphasizes the relative safety of rituximab in immunosuppressed patients. Transplant-related EBV lymphoproliferative disease has been successfully forestalled and treated with rituximab. Additionally, there is increasing evidence supporting the use of rituximab for primary CNS post- transplant lymphoproliferative disorder. In a retrospective multicenter review of 71 cases, 48% received rituximab as part of their treatment, including 8 patients who received rituximab alone. Patients receiving rituximab had improved 3-year progression free survival (40% vs. 22%, p= 0.02) and a trend towards a significant improvement in 3 year overall survival

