## 8 SAFETY REPORTING REQUIREMENTS/DATA AND SAFETY MONITORING PLAN

Adverse events while on-treatment and for 30-days after the last dose of therapy will be reported to the NCI IRB according to the guidelines below. All serious adverse events occurring while on study will be reported as outlined in section 8.2.1. Since all therapy will be standard, commercially available therapy, data will not be reported to other organizations. The Principal Investigator will be responsible for data safety monitoring.

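### No preset count of treatment-related deaths or primary-endpoint failures pauses accrual to the methotrexate cohort, so any halt would be ad hoc

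*Combined protocol and SAP*

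**What the plan says.** Section 6.1.3 states the target: "The goal of this limited size pilot trial is to enroll 15 evaluable patients who receive all treatment, including high-dose methotrexate". Up to 3 HAART-non-adherent patients may be replaced, so up to 18 could start main-cohort treatment. There is one analysis, "using a one-sided 0.1 alpha level exact test of binomial proportions, there is 88% power to rule out 30% with a satisfactory result", against an alternative in which "as many as 65% would be alive without recurrent lymphoma and without cognitive problems after two years". The comparator is historical: "it would be expected that only 25-30% of all such patients with this disease would be alive without recurrent brain lymphoma". Accrual is slow: "it is expected to take between 6 and 10 years to enroll 15 patients onto this trial in the main cohort". The section contains no interim look, futility rule or death boundary.

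Sections 3.5 and 3.11 govern treatment discontinuation and study exit for individual patients only. Section 8 says "The Principal Investigator will be responsible for data safety monitoring". Section 8.2.1 sends deaths other than those from progressive disease, and unanticipated problems, to the NCI-IRB and the Clinical Director within 7 days of the investigator learning of them. Section 8.2.2 requires adverse-event tables at continuing review. No count in either section is tied to accrual.

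Section 1.2.4.3 reports, from a randomized trial of CHOP plus HAART with or without rituximab, "Treatment related deaths occurred in 14% on the rituximab arm compared to 2% of those not receiving rituximab". It predicts that excess toxicity is unlikely with the present regimen and asks for vigilant monitoring, but gives no criterion.

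**The concern.** The protocol identifies a lethal-toxicity signal for one of its drugs in advanced AIDS and says it must be watched, but the statistical plan never turns this into a number. With 15 patients over 6 to 10 years (1.5 to 2.5 a year), there is time to respond to accumulating deaths or failures. Without a preset trigger, the point at which a run of deaths becomes too many is settled after it has occurred, starting with the investigator who runs the trial. The same holds for efficacy: enrolment can continue after the stated test can no longer succeed.

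**Working it through.** **Inputs.** From Section 6.1.3: n = 15, null 30%, alternative 65%, one-sided alpha 0.10, stated power 88%, accrual 6–10 years, up to 3 replacements. From Section 1.2.4.3: 14% and 2% treatment-related deaths. The death thresholds below are illustrative assumptions; the documents give none.

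**1. The plan's own figure.** With S successes in 15:
- P(S ≥ 7 | 0.30) = 0.131, above 0.10.
- P(S ≥ 8 | 0.30) = 0.050, so the exact test needs at least 8.
- P(S ≥ 8 | 0.65) = 0.887, matching the stated 88%.

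The power statement is right, and it assumes a single look at 15.

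**2. Deaths with no boundary.** At 14% the expected number is 15 × 0.14 = 2.1. P(≥ 3) = 1 − (0.86^15 + 15 × 0.14 × 0.86^14 + 105 × 0.14² × 0.86^13) = 1 − (0.104 + 0.254 + 0.290) = 0.35. At 2% the expected number is 0.3 and P(≥ 3) = 0.003.

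**3. Illustrative death rule:** pause at 2 deaths in the first 4, 3 in the first 10 or 4 in 15. Death counts only increase, so there is no pause exactly when D4 ≤ 1, D10 ≤ 2 and D15 ≤ 3. At 14%:
- Patients 1–4: P(0) = 0.5470, P(1) = 0.3562.
- Patients 5–10: P(0) = 0.4046, P(1) = 0.3952, P(2) = 0.1608.
- Patients 11–15: P(≤ 1) = 0.8533, P(≤ 2) = 0.9780, P(≤ 3) = 0.9983.
- D10 = 0, 1, 2 without an earlier pause: 0.2213, 0.3603, 0.2287.
- No pause: 0.2213 × 0.9983 + 0.3603 × 0.9780 + 0.2287 × 0.8533 = 0.768. Pause: 0.232.

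The same calculation at other rates:

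| True death rate | 2% | 5% | 10% | 14% | 20% | 30% |
|---|---|---|---|---|---|---|
| P(pause) | 0.3% | 2% | 11% | 23% | 45% | 76% |

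Mean enrolment at a 30% death rate is 8.7 instead of 15. A crossing at patient 15 is counted as a pause.

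**4. Power if a death pause became a permanent stop.** Take independent patients, each a success with probability 0.65, a treatment-related death with probability q, or another failure with probability 0.35 − q. P(S ≥ 8 and no pause) falls from 0.887 to about 0.87 at q = 5%, 0.81 at 10% and 0.72 at 14%.

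**5. Pause at the eighth failure.** Eight failures among 15 leave at most 7 successes. P(≥ 8 failures | 65% success) = 1 − 0.887 = 0.113, which is already the type II error, so no power is lost. At 30% success, P(eighth failure at patient n) = C(n−1, 7) × 0.7^8 × 0.3^(n−8). For n = 8 to 15 this is 0.058, 0.138, 0.187, 0.187, 0.154, 0.111, 0.072, 0.043.
- It occurs before patient 15 with probability 0.91.
- Expected enrolment is 11.3, a saving of 15 − 11.3 = 3.7 if outcomes were immediate.
- Opposite extreme (assumption): no failure is known until 24 months after enrolment, and accrual is even. Another 2 × 1.5 = 3 or 2 × 2.5 = 5 patients enter first. The saving is then 4 × 0.058 + 3 × 0.138 + 2 × 0.187 + 1 × 0.187 ≈ 1.2, or 2 × 0.058 + 1 × 0.138 ≈ 0.25.

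Deaths and recurrences can be known well before two years, so the true saving lies between these extremes.

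**The case against.** **Oversight is not absent.** A reader might infer that all 15 patients are treated whatever happens, or that the Principal Investigator alone watches safety. The documents do not support either. Section 8.2.1 puts reportable deaths before the IRB and Clinical Director within 7 days, often before the next enrolment at this pace, and Section 1.2.6 keeps the AIDS Malignancy Consortium informed. What is missing is a number.

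**14% is not the expected rate.** It comes from rituximab with CHOP in peripheral lymphoma. Section 1.2.4.3 explains that the present regimen avoids multiple lymphocytotoxic drugs, and reports nine AR-PCNSL cases treated with HAART, rituximab and various chemotherapies, with estimated one-year survival of 77.8%. This stands.

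**The protocol did not promise a stopping rule.** The phrase "limitations on the number of individuals exposed to potentially toxic and/ or ineffective treatments" in Section 6.1.1 explains why accrual is not enlarged to study gender and ethnicity. It should not be read as a commitment to a boundary.

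**This is a pilot for estimation.** The threshold of 8 is implied by the exact test and not written down, and Section 6.1.3 allows the approach to go forward on less. That is a good reason to make the failure trigger a review and not a termination. It does not answer the death question.

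**Failures must be counted carefully.** Section 7.1.1 describes replaceable patients as having relapsed, so of 8 raw failures as few as 5 might count. Section 5.3.6 also counts stable disease and elective discontinuation as treatment failure, although such a patient could still meet the two-year endpoint. Both points stand and shape the fix.

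**Cost.** It would be wrong to infer that pausing is free of power loss in general. That is true of the failure rule only.

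**Conclusion.** The omission is confirmed: nothing in Section 6.1.3 or Section 8 fixes a count at which accrual to the methotrexate cohort must pause. The sample-size calculation itself is correct. The gap matters because the protocol acknowledges a lethal-toxicity concern and accrual is slow enough for a trigger to work. Its size is modest. With 15 patients a death rule reliably detects only large excesses (76% at a true 30%, but 23% at 14%), and the failure rule saves at most about 3.7 patients at 30% success, fewer with outcome lag. These figures assume independent patients, the illustrative thresholds, and failures counted only among evaluable, non-replaced patients. The plan should be changed, but the finding does not imply that the trial is unmonitored or that 14% mortality is expected.

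**What to change.** Add one paragraph to Section 6.1.3, cross-referenced from Section 8:

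1. Accrual to the methotrexate cohort is paused pending IRB review when treatment-related deaths reach a preset number, with thresholds set by the sponsor and IRB. The rule of 2 in the first 4, 3 in the first 10 or 4 in 15 is one example with known properties. State who attributes deaths to treatment.
2. Accrual is also paused for review when 8 evaluable, non-replaced patients have definitively failed the two-year primary endpoint (death, recurrence or severe cognitive problems). Section 5.3.6 failures that leave that endpoint still attainable do not count.
3. State that both rules concern accrual only and do not alter the care of enrolled patients.

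No extra patients are needed. The example death rule carries a chance of pausing of 2% at a 5% death rate and 11% at 10%. If such a pause became permanent, power would fall as shown in the working, and the paragraph should say so. The failure pause costs no power, but if it became a stop there would be fewer patients for estimating the two-year fraction.
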